7.5.3. Weaning mechanical ventilation

Weaning procedures will be as per center practice.

Every morning (@08:00) that a patient has not started weaning procedures, reasons for not weaning are recorded in the CRF.

Date and time of first extubation which is maintained for more than 24 hours are recorded in the CRF.

7.6. ICU DISCHARGE - HOSPITAL STAY

Date and time of ICU discharge will be recorded in the CRF, as well as vital status at ICU discharge. Every morning (@08:00) that a patient has not been discharged from the ICU, reasons for not discharging are recorded in the CRF.

Renal (CL_{cr}, urine output) and hepatic (bilirubin, transaminases) function will be tested at 12, 24, and 36 hours after the beginning of Investigation Product infusion.

Before hospital discharge, laboratory tests will be performed. Results will be recorded in the CRF.

Length of hospital stay, vital status at hospital discharge and AEs will be recorded.

7.7. DRUG ADMINISTRATION IN THE ICU/HOSPITAL AND BLOOD SAMPLING FOR PHARMACOKINETIC ASSAY

Drug administration (maintenance dose) will continue during ICU/hospital stay.

Twenty-four hours after the start of the infusion, Infusion Bag No. 1 will be replaced by Infusion Bag No. 2. The removable label on Bag No. 2 will be detached and attached to the relevant page of the CRF. A blood sample will be obtained for pharmacokinetic assay @ 24±6 hours.

Infusion of Investigational Product will continue up to 48 hours. Immediately before the infusion is terminated, a blood sample will be obtained for pharmacokinetic assay.

An additional blood sample will be obtained in the interval 2-6 hours after the end of infusion.

Blood sampling for pharmacokinetic assay will be via an indwelling intravenous (or intra-arterial, if already in place) cannula or by direct venipuncture. On each time point, a 6 mL sample will be taken into lithium heparin monovettes. Details of sample handling are reported in Appendix 1.

Time of bag replacement, end of infusion, and blood sampling will be recorded in the CRF.

7.8. MONTH 1 POST-TRANSPLANT

Patient will attend the center for study assessment at month 1 (at least 30 days post transplant). The following measurements will be performed as per center practice and recorded in the CRF:

- FEV₁, FVC. Actual date of assessment will be recorded in the CRF.

Any AEs that occurred during the interval i.e. since 10 days after the end of study drug administration or since hospital discharge (if applicable), and that the Investigator assesses as at least possibly related to the Investigational Product, will be recorded at this visit, as well as patient vital status.

7.9. MONTHS 6 AND 12 POST-TRANSPLANT

Patient will attend the center at months 6 and 12 +/- 2 weeks post-transplant. The following measurements will be performed as per center practice (unless otherwise specified) and recorded in the CRF:

- FEV₁, FVC, BOS score will be assessed at each visit. BOS score will be evaluated according to Estenne et al. (2002).
- Acute, biopsy proven rejection episodes diagnosed according to Yousem et al. (1996). Cumulative assessment at each visit.

For all measurements above, actual date of assessment will be recorded in the CRF. Diagnosis and treatment of acute rejection, if any, will be also recorded in the CRF.

Patient vital status, as well as any AEs occurring during the intervals between study visits that the Investigator assesses as at least possibly related to the Investigational Product will be recorded at each visit.

7.10. EARLY PATIENT WITHDRAWAL

7.10.1. Withdrawal criteria

Patients will be informed that they have the right to withdraw from the study at any time, without prejudice to their medical care, and are not obliged to state their reasons. Any withdrawals must be fully documented in the CRF and should be followed up by the Investigator.

Additionally, the Investigator may withdraw a patient at any time if (s)he considers this to be in the patient's best interest. Also, a patient might be withdrawn from the study, at the Investigator's judgment, in case of protocol violations, including (but not limited to) non-compliance with study procedures, patient lost to follow-up or administrative reasons.

Patients **must** be annulled from the study for the following reasons:

- Patient was randomized, but did not receive the Investigational Product,
- Patient was randomized, but did not proceed to lung transplantation.

If a patient fails to return to the center for a scheduled visit, attempts should be made to contact the patient to ensure that the reason for not returning is not an AE that may at least possibly be related to Investigational Product. Likewise if a patient declares his/her wish to discontinue from the study e.g. for personal reasons, an attempt should be made to establish that the true reason is not an AE (bearing in mind the patient is not obliged to state his/her reasons).

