6.2. DOSE, ROUTE AND SCHEDULE OF INVESTIGATIONAL PRODUCT ADMINISTRATION

According to the parallel-group design, patients will receive either repertaxin or placebo as determined by a previously generated randomization schedule.

An initial 'loading dose' of repertaxin of 4.488 mg/kg body weight/hour will be administered over 30 minutes followed by a maintenance dose of 2.772 mg/kg body weight/hour lasting 47.5 hours. Placebo will be volume matched saline.

The study drugs will be administered as a continuous i.v. infusion into a (high flow) central vein, by an infusion pump adequate to provide reliable infusion rates (see below), as per treatment schedule. Total infusion volume will not exceed 500 mL/24 hours.

The infusion will start approximately 2 hours before the anticipated time of reperfusion. For the purpose of this trial, reperfusion is defined as "the time of resumption of blood flow after vascular de-clamping of the first allograft". If cardiopulmonary bypass is used, the time of reperfusion is when the patient comes off the bypass, unless partial de-clamping occurs prior to complete stop of cardiopulmonary bypass. The surgeon will identify the time to start study drug infusion. In most instances, this time will be close to the time of the incision that begins the operation.

The loading and maintenance doses will be given using the same dosing solution (repertaxin 12.65 mg/mL), but the pump rate will be altered to provide an infusion rate of approximately

0.35 mL/kg/hour and 0.22 mL/kg/hour, respectively. Actual infusion rate (mL/hour), adjusted to body weight, is tabulated in Appendix 3. Figures in the appendix represent mathematical rounding of original infusion rates derived from the following formula:

$$\text{Infusion rate (mL/hour)} = \frac{\text{dose (mg/kg/hour)} \times \text{body weight (kg)}}{12.65 \text{ mg/mL}}$$

Such a rounding affects actual administered dose/kg/hour by less than 1%.

Technical characteristics of the infusion pump should include infusion rate covering the range from 6.6 to 31.9 mL/hour, in 0.1 mL/hour increments, and capacity in excess of 600 mL/day.

6.3. CRITERIA FOR SCHEDULE ADJUSTMENT/DOSE-MODIFICATION/ DISCONTINUATION OF INVESTIGATIONAL PRODUCT

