7.10.2. Replacement policy

Only patients withdrawn due to one of the following reasons will be replaced:

- Patient was randomized, but did not receive any Investigational Product,

- Patient was randomized, but did not proceed to lung transplantation.

Should a patient be replaced, his/her number will not be reallocated. A new patient will be enrolled and assigned the next number available.

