9.3. ANALYSIS POPULATION

The Safety population will consist of all patients who received any study medication, and will be based on the treatment actually received. The Safety population will be used to present the demographic and baseline data, and all safety data.

The Intent to Treat (ITT) population will consist of all patients who received any study medication and the transplant, and will be based on the treatment randomized, regardless of the treatment actually received.

The Per-Protocol (PP) population will consist of all patients in the ITT population who did not have any major protocol violations, defined to be:

- Patient who started study drug infusion after reperfusion, i.e. after vascular de-clamping of the first allograft,
- Patients who did not receive the study medication for at least 24 hours,
- Patients without data for PaO₂/FiO₂ ratio at 0 and 24 hours, while on mechanical ventilation,
- Patients who receive Orthoclone OKT3 or Campath induction immunosuppression,

The primary and secondary efficacy analyses will be presented for the ITT population, primarily, and confirmed by the PP population.

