## 3 STUDY DESIGN

### 3.1 Overview

This is a phase 2, multi-center, randomized, double blind, placebo-controlled, parallel group study of repertaxin in the prevention of PGD after lung transplantation. The study will involve 100

patients undergoing single or bilateral lung transplant who will be randomized to receive either repertaxin or placebo via continuous intravenous (i.v.) infusion administered over 48 hours. Patients randomized into the study who do not go on to receive study drug or lung transplant will be replaced therefore the total number of patients randomized may exceed 100. Patients will be followed for 12 months post-transplant but the majority of study assessments are performed during the intensive care unit (ICU) and hospital stay immediately after surgery.

Patients will be selected for entry into the study from those listed on the center's lung transplant waiting list. Inclusion/exclusion criteria (as listed in protocol sections 5.1 and 5.2), disease history, extrapulmonary site of infection, significant medical history, vital signs, renal and hepatic function, laboratory safety tests and donor information will all be assessed prior to randomization to ensure patient eligibility.

The lung transplant surgery will be performed according to the center's standard practice. The study drug infusion will start approximately 2 hours before the anticipated time of reperfusion of the first allograft. A loading dose will be administered for the first 30 minutes, followed by a maintenance dose for the remaining 47.5 hours of administration.

After completion of surgery, patients will be admitted to an ICU and blood gases ( $\text{PaO}_2$ ,  $\text{FiO}_2$  and  $\text{PaO}_2/\text{FiO}_2$  ratio) will be measured on admission (time 0) and at 24, 48 and 72 hours post ICU admission or until extubation whichever occurs earlier. Chest x-rays, renal and hepatic function and PK sampling will be measured at defined time points within the 72 hours following ICU admission. Vital signs (BP and HR) and cardiopulmonary measurements will be assessed at defined time points within the 5 days post ICU admission or until ICU discharge (or PA catheter removed) whichever occurs earlier. Further patient assessments are made at ICU discharge and hospital discharge.

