### 9.2 Patient Disposition

The number and percentage of patients screened, randomized and treated in the study will be presented, together with the number and percentage of patients who withdrew from the study prematurely prior to Month 1 and a breakdown of the corresponding reasons for withdrawal. The number and percentage of patients included in each of the ITT, PP and safety analysis populations will also be included. Screening data recorded for patients who do not proceed to transplant with study drug administration will be listed separately in the report. The exact format of the listings will be discussed with Dompé when the total number of patients randomized but not treated/transplanted is known.

A tabulation of the number and percentage of patients randomized at each center will be presented.

All data relating to study completion or withdrawal and inclusion in the analysis populations will also be listed.

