#### 9.5.2.5 Mortality

Frequency counts and percentages for the number of patients who die while in ICU and also the number and percentage of patients who die within the first 30 days post-transplant (derived as latest date of reperfusion + 30) will be presented by treatment group. This table will be presented for the ITT population only.

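### The rule to annul and replace non-transplanted patients makes no exception for those already infused, which conflicts with the Safety population; separately, a death between infusion start and transplant cannot enter the mortality table

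*Protocol*

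**What the plan says.** **Annulment and replacement.** Protocol 7.10.1 states that patients must "be annulled from the study for the following reasons", then lists two reasons as separate items: no Investigational Product received, and "Patient was randomized, but did not proceed to lung transplantation". Protocol 7.10.2 repeats the pair as the only grounds for replacement: "Only patients withdrawn due to one of the following reasons will be replaced". SAP 3.1 agrees: "Patients randomized into the study who do not go on to receive study drug or lung transplant will be replaced". The protocol does not define annulment. SAP 3.3 uses the word for the drug box.

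**Timing of exposure.** Protocol 6.2 starts the infusion about two hours ahead of expected reperfusion, at a time chosen by the surgeon: "In most instances, this time will be close to the time of the incision that begins the operation". Dosing therefore begins before the graft is in place.

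**Populations.** Protocol 9.3: "The Safety population will consist of all patients who received any study medication, and will be based on the treatment actually received". SAP 6.3 agrees. Neither makes transplantation a condition. The ITT population (Protocol 9.3, SAP 6.1) requires both study drug and a transplant.

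**Reporting.** SAP 9.2: "Screening data recorded for patients who do not proceed to transplant with study drug administration will be listed separately in the report". Listing 4.21.x covers screening data for patients randomized but not treated or transplanted. SAP 9.5.2.5 counts deaths in the ICU and deaths within 30 days of the last reperfusion date, and adds: "This table will be presented for the ITT population only".

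**The concern.** A recipient can be infused and then not transplanted, for example because the operation is abandoned or the patient dies before implantation. Read literally, Protocol 7.10.1 obliges the site to annul that patient. The Safety definition obliges the analyst to count the same patient. If the site takes annulment to end data collection, the analyst has a Safety-population member with no adverse events, no SAEs and no 30-day vital status.

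The group is small, but its loss would not be neutral. These patients leave after exposure, possibly because of something that happened after exposure. Protocol 8.5 also asks the DMC to monitor deaths in both arms.

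There is a second, independent gap. A patient who dies between infusion start and transplant is outside the ITT population and has no reperfusion date, so the death cannot appear in the SAP mortality table, however annulment is worded.

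**Working it through.** **1. The plan's own figure.** The documents give no number on this point. Their only related figure is power (Protocol 9.1, SAP 3.2): 50 per arm, SD 137 mmHg, one-sided 0.05. The standard error is 137 × √(2/50) = 27.4. The noncentrality is 70/27.4 = 2.55 or 50/27.4 = 1.82. A t-test on 98 degrees of freedom gives 81.4% and 56.6%, against the stated 81% and 56%. Replacement preserves the number transplanted, so the point does not touch these figures.

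**2. Is there exposure before transplant?** At the rates in Protocol 6.2, two hours of infusion delivers 4.488 × 0.5 + 2.772 × 1.5 = 6.40 mg/kg. The full course is 4.488 × 0.5 + 2.772 × 47.5 = 133.9 mg/kg, so about 4.8% of it is given before a reperfusion that occurs on schedule. The category of exposed but not transplanted is therefore real.

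**3. One such patient, traced through the plan.**

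| Provision | Treatment of a dosed, non-transplanted patient |
|---|---|
| Protocol 7.10.1, 7.10.2; SAP 3.1 | Annulled (protocol) and replaced (protocol and SAP); no exception for exposure |
| Protocol 9.3; SAP 6.3 | In the Safety population |
| Protocol 9.3; SAP 6.1 | Not in the ITT population |
| Protocol 8.3.1 | Adverse events recorded from the first day of drug; no transplant condition |
| Protocol 7.8; SAP 5 | Month 1 is dated from transplant, so no defined 30-day assessment |
| SAP 9.6.2, Table 3.2.1.1 | A death is counted in the Safety-population AE summary, if the data exist |
| SAP 9.5.2.5, Table 2.6 | A death is not counted |
| SAP 9.2, Listing 4.21.x | Screening data listed apart, together with never-dosed patients |

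Protocol 6.3.2 offers a contrast. Patients who stop study drug early are expressly kept under observation by default. No equivalent sentence covers this group.

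**4. Effect on a death rate (illustration).** Assume *d* deaths among 50 transplanted patients in an arm, plus *k* exposed patients who die without a transplant. The ITT table shows d/50; an all-exposed table shows (d + k)/(50 + k).

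| d | ITT | k = 1 | k = 2 | k = 3 |
|---|---|---|---|---|
| 2 | 4.0% | 3/51 = 5.9% | 4/52 = 7.7% | 5/53 = 9.4% |
| 5 | 10.0% | 6/51 = 11.8% | 7/52 = 13.5% | 8/53 = 15.1% |

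**5. Effect on an SAE rate.** Adding one patient with an SAE moves x/50 to (x + 1)/51. That is 1.96 points when x = 0, and 0.98 points when x = 25 (50.0% to 51.0%).

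**6. How likely is at least one case?** The documents give no rate. If the chance per patient is assumed to lie between 0.5% and 5%, the chance of at least one case in 100 patients is 1 − 0.995^100 = 39% to 1 − 0.95^100 = 99%.

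**The case against.** The strongest reply is that no rule in the plan removes an exposed patient from the safety data. This stands. Both Safety definitions include such patients. Adverse-event recording follows drug administration, and all SAEs must be reported (Protocol 8.3.1, 8.4.1). Protocol 7.10.1 itself asks for withdrawals to be documented and followed up. SAP 9.1 has all CRF data listed, and Listings 2.6.5 and 4.15 cover vital status and deaths. Table 1.3 reports, within the Safety population, deviations that exclude patients from ITT or PP; for a dosed patient the only route out of ITT is having no transplant. A reader might infer that exposed patients *would* be dropped. The documents support only that they *could* be.

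A reader might also take SAP 9.2 and Listing 4.21.x to mean that nothing beyond screening data will be reported. The SAP does not say that. It says where screening data go and leaves the format open.

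It can be argued that the mortality table matches its endpoint, since Protocol 4.2.1.2 defines mortality from transplant and a never-transplanted patient has no such period. That is fair, and it is why an additional safety table is proposed while the efficacy table stays as it is. The gap comes from the ITT definition, the ITT-only restriction and the reperfusion clock. Rewriting the annulment rule would not close it.

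Finally, failing to proceed to transplantation might be read as surgery never starting, which would leave most infused patients outside the rule. That reading is possible, but the text does not state it, and the first listed reason already covers anyone who received no drug.

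**Conclusion.** The conflict is real and unresolved in the text: a mandatory annulment rule with no exception for exposure stands against a Safety population of everyone exposed. A site and an analyst, each following the document, could treat the same patient differently. The consequence is a risk of incomplete AE, SAE and 30-day vital-status data. The plan does not direct that loss.

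A reader might infer that intra-operative deaths in general are at stake. They are not: a patient who dies after reperfusion has been transplanted and belongs to both the ITT and Safety populations. Only deaths or abandoned operations between infusion start and transplant are affected.

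The mortality-table gap is certain for such a death, which would appear only in the Safety-population AE death count, and only if the data are kept. With one such death in an arm, 4.0% becomes 5.9%, or 10.0% becomes 11.8%, on the assumed baseline of 2 or 5 deaths among 50. The number of affected patients and the baseline death rates are assumptions. Power and sample size do not change.

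**What to change.** 1. In Protocol 7.10.1, define annulment and limit it to patients who received no study drug. Under 7.10.2, replacing an exposed, non-transplanted patient for the efficacy count may continue.
2. State in the protocol that exposed, non-transplanted patients stay in the Safety population, with AE and SAE recording over the period in 8.3.1 and vital status at 30 days.
3. In SAP 9.2 and Listing 4.21.x, restrict the separate screening-data listing to never-dosed patients.
4. Keep the ITT mortality table and add a Safety-population death table by treatment received, timed from infusion start.

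The cost is a short protocol clarification, a wording change in the SAP, one extra table, and a fuller CRF for a few patients. According to SAP 1.1, about 60 patients had been randomized at the time of writing and the plan was to be finalized before database lock, so the SAP changes can be made before unblinding.

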7.10.2. Replacement policy

Only patients withdrawn due to one of the following reasons will be replaced:

- Patient was randomized, but did not receive any Investigational Product,

- Patient was randomized, but did not proceed to lung transplantation.

Should a patient be replaced, his/her number will not be reallocated. A new patient will be enrolled and assigned the next number available.

8. ADVERSE EVENTS

8.1. DEFINITIONS

8.1.1. Definition of an Adverse Event

An adverse event (AE) is defined as any untoward medical occurrence in a patient or clinical investigation subject administered a pharmaceutical product, which does not necessarily have a causal relationship with this treatment. An AE can therefore be any unfavorable and unintended sign (including an abnormal laboratory finding), symptom, or disease temporally associated with the use of a medicinal (investigational) product, whether or not related to the medicinal (investigational) product [*Clinical safety data management: Definitions and Standards for Expedited Reporting*].

8.1.2. Definition of a Serious Adverse Event

A Serious Adverse Event (SAE) is defined [*Clinical safety data management: Definitions and Standards for Expedited Reporting*] as any untoward medical occurrence that at any dose:

- results in death,
- is life-threatening (i.e. the patient was at risk of death at the time of the event. It does not refer to an event which hypothetically might have caused death if it were more severe),
- requires inpatient hospitalization or prolongation of existing hospitalization,
- results in persistent or significant disability/incapacity,
- is a congenital anomaly/birth defect,
- is an important medical event that based upon appropriate medical judgment, may jeopardize the patient and may require medical or surgical intervention to prevent one of the outcomes listed above.

8.2. EMERGENCY PROCEDURES

All AEs should be followed-up to determine outcome of the reaction. The Investigator should follow up the event until resolution or stabilization of the condition. It is the Investigator's responsibility to assure that the subjects experiencing AEs receive definite treatment for any AE, if required.

The treatment allocation for each patient will be provided in individual sealed envelopes. The location of these envelopes must be communicated to relevant study site staff and documented in the Investigator file. An envelope should only be opened in case of emergency where knowledge of the double-blind treatment may influence the further care of the patient. All such envelopes (both opened and unopened) will be collected by PPD as each patient completes the study. If an envelope is opened for any reason, the Investigator will notify PPD immediately and a record will be kept of when it was opened, by whom and why.

